In months 1 to 8, we will conduct key informant interviews with primary care patients (up to N=15), clinicians and administrators (up to N=15) to learn how the intervention, originally designed for a resourced, subspecialty setting, should be refined to meet new user needs. These activities will be guided by the Agency for Health Care Research and Quality's MCC Model and informed by the expertise of the Northwestern Pepper Center's **Design, Measurement, and Analytics Cores**.

Aim 2: Assess the PATTERN intervention's feasibility and acceptability for use in primary care.

In months 9 to 24, we will implement a 2-arm, patient-randomized pilot study at one or more NM internal medicine practices. Adults over 65 (N=80) with an upcoming primary care visit (within the next ~1 week, with MCC and polypharmacy, defined as taking ≥ 8 chronic medications, will be recruited over 6 months, and followed for 6 months (n=40 per study arm). Interviews will evaluate participants' experiences with the PATTERN intervention, regimen knowledge, and adherence (via self-report) utilizing a post-visit survey. The specific flags per question on the survey (the point at which someone is classified as having a phenotyped adherence concern) will be determined by the participating practice. Fidelity (receipt of portal assessment and time to completion, care response to adherence concerns, etc.) and clinical outcomes will be captured in the EHR.

BACKGROUND:

The population of adults over 65 in the U.S. is growing at a rate 3-fold higher than those under 65, presenting unique challenges to primary care practices. Older adults are more likely to have multiple chronic conditions (MCC), and associated polypharmacy (often defined as taking ≥ 5 prescription medications). As a result, problems with treatment adherence are common; prior estimates have found 30 to 50% of community-dwelling, older adults over 65 demonstrate poor medication adherence. These individuals are at subsequent greater risk for suboptimal treatment benefits and adverse drug events, which are also more likely to occur in primary vs. specialty care, and among older adults with MCC. Studies have also shown that inadequate adherence is associated with poorer health-related quality of life, higher healthcare costs and increased mortality risk.

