We will adapt the already-built TAKE IT strategy for use in primary care, targeting older adults with MCC and polypharmacy (using Medicare Part D medication therapy management criteria of ≥ 8 medications). This intervention, renamed as the PATTERN study (**P**henotyping **A**dherence **T**hrough **T**echnology-**E**nabled **R**eports and **N**avigation) will be pilot tested at one or more Northwestern Medicine (**NM**) primary care practices to determine its acceptability, feasibility, and preliminary fidelity.

STUDY ENDPOINTS:

Regimen adherence utilizing a post-visit survey as measured by ARMS- D and/or ASK-12 is the **primary outcome** of interest.

Variable	Instrument(s) or Measure(s)	Source	Timing & Window		
			Screener	Post Visit Survey	6M
			Phone	Phone	
Outcome Measures					
Medication Adherence	ASK-12 and ARM-D	self-report		x	
Clinical outcomes	HbA1c	chart / EDW		x	x
	Cholesterol panel	chart / EDW		x	x
	systolic/diastolic blood pressure	chart / EDW		x	x
Acceptability	Qualitative	Theoretical Framework of Acceptability		x	

STU#: STU00217555

Secondary outcomes include clinical outcomes (e.g. A1c, blood pressure, cholesterol panel). Relationships between adherence and potential confounders (age, comorbidity, regimen complexity, internet use, dose of intervention, health literacy, patient activation, social support) will also be examined. Acceptability and fidelity/feasibility will also be examined. This may include examining how many participants in the intervention arm completed the adherence questionnaire and how many of those indicating an adherence challenge were responded to in some way by the clinic.

STUDY INTERVENTION

The goal of TAKE IT is to optimize adherence and to detect problems earlier to improve health outcomes in kidney transplant centers. TAKE IT includes the following intervention components that will be adapted and piloted for use in the PATTERN study for primary care among adults aged 65 and older with polypharmacy and multiple chronic conditions:

1. **An adherence assessment** that requests patients to report on their medication use, providing a link between the health center and patient beyond routine in-person visits. This assessment will identify patients at risk of non-adherence and categorize their adherence concern(s) as: cognitive, psychological, regimen, medical, social, economic.

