turn their video cameras off so only their audio is recorded. Specifically, the Northwestern research team will record the interview portions where participants are offering suggestions or giving us feedback on the adaptation of the TAKE IT intervention into the PATTERN study (as described above). We will not record any identifiable information (ex: medical records or responses to demographic questionnaires). Due to Zoom recording recommendations made by NUIT, interviews conducted with the Zoom software will be recorded to the Zoom Cloud. Recording to the Zoom Cloud, rather than directly to one's computer, prevents the recorded files from becoming corrupted and diminishing the quality of the recording (ex: failed recording where not everything is recorded).

The Zoom Cloud or Microsoft Teams recordings will be downloaded and saved onto secure FSM department servers. Only authorized research personnel will have access to the data. The recordings may be used solely by the Northwestern research team for analysis purposes only. Recordings from the qualitative research activities will be analyzed using a rapid approach to qualitative analysis. De-identified notes may be taken as needed. The recordings and notes will be stored on the FSM department servers for the duration of the study. At the conclusion of the study, all recordings will be destroyed.

If a participant is not willing to be audio recorded, then they will be unable to participate in the Aim 1 study activities. No pilot study activity will involve audio or visual recording; those activities will take place over the phone through a Northwestern phone line.

Aim 2: Pilot study (N=80; n=40 per arm)

For **Aim 2**, we will conduct a patient-randomized controlled trial at one Northwestern Medicine primary care practice and followed for 6 months. A total of 80 participants will be recruited and randomly assigned via REDCap once a primary care appointment is scheduled to either the PATTERN arm or usual care (N=80, n=40 per) arm. Usual care refers to the normal standard clinical practices at the participating practice(s).

Research activities (described in detail below) will include an adherence assessment (for those in the Pattern arm) and a post-visit survey (for both arms) which will be conducted over the phone via a Northwestern phone line.

Adherence assessments (part of the intervention)

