Adherence assessments will be automatically delivered to patients randomized to the intervention arm with an upcoming appointment to report medication challenges via MyChart.

Post-visit interviews

- 1) Potential participants who have an upcoming primary care visit (within the next ~1 week) will be called via a Northwestern telephone line to be recruited for the study. After confirming eligibility via phone, the participant will provide an electronic informed consent or verbal consent prior to participation. Individuals for whom have technology issues and electronic consent is not practical due to technological challenges, will be subject to verbal HIPAA/Alteration of HIPAA. The RC will schedule the post-visit survey

STU#: STU00217555

about 2 to 4 weeks after the patient attended their primary care visit and will inform the participant that it will be about a ~30 minute phone interview.

- 2) The RC will schedule interviews at the convenience of patients.
- 3) Patients may receive a phone call as a reminder to attend their scheduled study visit.
- 4) At the end of the phone interview there are open-ended questions for participants randomized to the intervention. These will be audio recorded, with the participant's permission, using a handheld audio recorder, Zoom, or Teams. The participant will be reminded that only that portion of the interview will be audio recorded.
- 5) The RC will turn off the audio recording, thank the patient, and confirm the delivery process for compensation.
- 6) The RC will thank the patient and confirm the delivery process for compensation.

Aim 2: Audio Recording

All participants randomized to the intervention will be asked a short series of open-ended questions to assess their acceptability of the intervention. These open-ended questions will be audio recorded using a hand-held audio recorder, Zoom, or Teams. Prior to recording the interview, study participants will be reminded that a portion of the interview will be audio recorded. Specifically, the Northwestern research team will record the end of the interview where participants are discussing their acceptability of the intervention. We will not record any identifiable information (ex: medical records or responses to demographic questionnaires).

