Potentially eligible patients will be identified via the EHR. A report containing contact information (name, dob, gender, phone number, address, email, medical record number, clinic name, clinic date (Aim 2), and primary care provider name) will be downloaded from the EDW. An RC will review the report and then mail a letter to patients on the list, notifying them that a trained Northwestern RC will be telephoning to invite them to participate in a study. Patients will be given the opportunity to opt out of being contacted by calling a hotline number and leaving a message. Seven days after the letters have been mailed, an RC will call patients who did not opt out to ask screener questions to determine eligibility and, if eligible and interested, schedule their one-time interview (Aim 1).

An RC will contact potential participants via phone using a Northwestern phone line to invite them to participate in a study. Potential participants will be informed about the study and if

STU#: STU00217555

interested, the RC will continue to ask screener questions to determine eligibility and, if eligible consent and randomize, and schedule their one-time interview (Aim 2).

COMPENSATION FOR PARTICIPATION IN RESEARCH ACTIVITIES

Participants who consent to participate in the Aim 1 Key Informant Interviews, and those who participate in the Aim 2 pilot testing activities will be compensated for their time and effort. Participants will be paid at the completion of the interview via the PNC Stored Value Visa Card program (physical gift card) or via the Northwestern Visa Prepaid Card program (virtual gift card). Participants will be asked which payment type they prefer.

Study Activity	Payment Amount
Aim 1: Key Informant interviews with clinicians and administrators	\$100
Aim 1: Key Informant interviews with patients	\$30
Aim 2: Pilot study participation	\$50 (post-visit interview)

WITHDRAWAL OF PARTICIPANTS

There are no anticipated circumstances when a participant would be withdrawn from the study without their consent.

Participants can choose to withdraw from the study at any time. If a participant chooses to withdraw from the research, any data collected up until the point of withdrawal will still be utilized as it will not include identifying information. They will then not be contacted for further interviews or visits.

RISKS TO PARTICIPANTS

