Patient Characteristics. We will include a socio-demographic/health questionnaire, and the Tangible Social Support survey to assess the extent/quality of social connections. The Consumer Health Activation Index (CHAI) will be included, and patients will be asked about their internet use.

Regimen Complexity. EHR data will identify the number of prescription medications an individual has been prescribed. This will serve as a proxy for medication regimen complexity.

Fidelity (Process Measures).

Receipt of adherence assessments. During the post-visit survey, the RC will ask whether patients received the adherence assessments. We are only collecting these 1-time at the follow-up interview (not longitudinally).

Use of Patient Portal. During the post-visit interview, the RC will inquire whether patients used the portal to complete the adherence assessment which will be verified using EHR data.

Care Alert Notification. We will review EHR data on care alerts, and nurse follow up to identify whether adherence concerns were addressed by the care team. The RC will also ask patients if they received follow up, by whom, and what services were provided.

Effectiveness Outcomes. We will collect data on an array of knowledge, behavioral, and clinical outcomes.

Medication Adherence. Adherence will be measured using: 1) ARMS-D and/or ASK-12.

Clinical Outcomes. *Blood pressure* (continuous SBP; control (y/n): SBP<140 & DBP<90) and *glycemic control* (*HbA1c*) will also be examined in those with hypertension and diabetes. The cholesterol panel will also be included.

PROVISIONS TO MONITOR THE DATA TO ENSURE THE SAFETY OF PARTICIPANTS

NA: This study does not include more than minimal risk.

PROVISIONS TO PROTECT THE PRIVACY INTERESTS OF PARTICIPANTS

Participants will be informed in all cases about their rights as research subjects. They may withdraw at any time during the study without penalty or loss of any healthcare benefit or service to which they are entitled. Patients will be assigned a unique identification number. We will also attempt to reduce shame and performance anxiety as a result of interviews through extensive training of the interviewer(s).

Data collected includes online and verbal consent forms for Aim 1 and for Aim 2. It also contains information collected during the study interviews (demographics, audio recordings of key informant interviews (Aim 1), survey/interview information (Aims 1 and 2), as well as clinical data from the EDW (Aim 2).

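### The coordinator role that randomises also takes the self-reported primary outcome, in a call with arm-revealing questions, and neither masking nor question order is stated

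*Protocol*

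**What the plan says.** **Allocation.** Under Recruitment Methods (Aims 1 and 2: Recruitment of patients), the RC phones the patient, and "the RC will continue to ask screener questions to determine eligibility and, if eligible consent and randomize, and schedule their one-time interview (Aim 2"). Under Procedures Involved (Aim 2: Pilot study), patients are "randomly assigned via REDCap once a primary care appointment is scheduled to either the PATTERN arm or usual care".

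**Primary outcome.** Study Endpoints names it as "Regimen adherence utilizing a post-visit survey as measured by ARMS- D and/or ASK-12". Objectives (Aim 2) describes "adherence (via self-report) utilizing a post-visit survey". Procedures Involved describes "a post-visit survey (for both arms) which will be conducted over the phone via a Northwestern phone line". The steps listed under Post-visit interviews are carried out by the RC.

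**Other content of the same call.** Measures, Fidelity (Process Measures), states: "During the post-visit survey, the RC will ask whether patients received the adherence assessments". It adds RC questions on whether the portal was used to complete the assessment, and on what follow-up was received, from whom and with which services. Data Management and Confidentiality ties the message and portal questions to patients receiving PATTERN. Post-visit interviews adds: "At the end of the phone interview there are open-ended questions for participants randomized to the intervention".

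**Safeguards.** The open-ended block is the only part of the call with a stated position. The only interviewer measure is training to limit shame and performance anxiety (Provisions to Protect the Privacy Interests of Participants). The protocol does not mention masking the interviewer, separating the randomising and interviewing tasks, or placing the adherence scales before the fidelity items.

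**The concern.** The primary outcome is a patient's own account given to a live interviewer, so it is sensitive to how questions are put and to what was asked just before. Two routes are open.

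- **Interviewer knowledge.** An interviewer who knows the arm, from randomising the patient or from earlier answers in the call, may prompt, clarify or record differently by arm.
- **Question order.** If questions about the assessment and the clinic's response come first, they may change how intervention patients answer the scales. They have less to act on in usual care, where no assessment was sent.

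Either route would produce a difference between arms that the planned chi-square or t-test cannot tell from an intervention effect. The endpoint table, as it reads, schedules adherence only at the post-visit survey and lists no objective adherence measure, so there is little against which to detect such a shift afterwards. The protocol also lets a non-significant trend trigger effect-modification analyses, and the pilot is meant to inform a multi-site trial. A modest artefact could therefore influence later decisions.

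**Working it through.** **Step 1: does the protocol text support each link?**

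| Link | Where | Finding |
|---|---|---|
| RC role randomises | Recruitment Methods | Stated |
| RC role runs the post-visit call | Post-visit interviews; Measures | Stated |
| The call yields the primary outcome, by self-report | Objectives; Study Endpoints; Procedures Involved | Stated |
| The assessment goes only to the intervention arm | Procedures Involved, Adherence assessments | Stated |
| The same survey asks about receipt and portal use | Measures | Stated |
| The RC also asks about follow-up | Measures | Stated; by context, in the same call |
| Scales come before fidelity items | Nowhere | Order not given |
| Interviewer masked, or a different person from the randomiser | Nowhere | Not given |

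The fidelity items threaten masking whichever way the text is read. If they go to both arms, as Measures suggests, the answers tend to disclose the arm. If they go only to patients receiving PATTERN, as Data Management and Confidentiality suggests, the interviewer must know the arm to ask them.

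**Step 2: the plan's own figure.** Data Management and Confidentiality gives 80 accrued, 90% retention and a minimum of 72 analysed. 80 × 0.90 = 72, which reproduces. With 1:1 allocation, 72 / 2 = 36 per arm. The same sentence allows consenting to continue until there are 80 interviews, so 40 per arm is shown as well.

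**Step 3: what a shift could do (illustration).** The protocol gives no bias size, SD or alpha. Assumptions: no true effect, two-sided alpha 0.05, and a shift of *d* SD between arms arising only from the interview.

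- Noncentrality = *d* × √(*n*/2), with 2*n* − 2 degrees of freedom.
- Rejection probability = P(|T| > t₀.₉₇₅), with T noncentral t.
- For *n* = 36: √18 = 4.243, df = 70. For *n* = 40: √20 = 4.472, df = 78.

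| Assumed shift *d* | Noncentrality, *n* = 36 | Rejection rate, *n* = 36 | Rejection rate, *n* = 40 |
|---|---|---|---|
| 0 | 0 | 5.0% | 5.0% |
| 0.1 SD | 0.424 | 7.0% | 7.3% |
| 0.2 SD | 0.849 | 13.3% | 14.3% |
| 0.3 SD | 1.273 | 24.1% | 26.3% |

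The test is two-sided, so the rates are the same whichever arm the shift favours.

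**The case against.** The best reply is that much of this rests on silence. Measures lists items by topic and sets no order; order usually sits in the survey instrument, which is not shown. The one position the protocol does fix, the open-ended block at the end, is protective. Allocation runs through REDCap and the assessment is delivered automatically, so the RC need not carry the arm into a call 2 to 4 weeks after the visit. This is also a small feasibility pilot that claims no masking, and its clinical outcomes come from the chart or data warehouse.

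Much of that stands, and it rules out several stronger readings that a reader might infer:

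- **That the same person randomises and interviews.** The text shows the same role. Coordinators appear in the plural under Inclusion and Exclusion Criteria, so two people may be involved.
- **That the fidelity items come before the scales.** The order is unstated. It may already be sound in the survey script.
- **That any bias must favour PATTERN.** The documents do not establish this. The intervention invites patients to report medication problems, so priming could equally make them disclose more non-adherence.
- **That the error rate is 7% to 24%.** Those rates follow from assumed shifts and would arise in any trial of this size with the same shifts.

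The reply does not remove the point. Who makes the call and what it contains are conduct matters that the protocol itself sets, so a separate analysis plan would not settle them. A second coordinator would still learn the arm if the fidelity items came first. And although this is a pilot, the protocol names adherence as primary and compares it by arm.

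**Conclusion.** The concern holds in limited form. As written, a subjective primary outcome is collected by a role that can know or learn the arm, in a call containing arm-revealing questions, with no stated masking and no stated order that protects the scales. Avoidable interviewer or question-order bias can therefore enter the arm comparison, in either direction.

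The size is unknown. The 7% / 13% / 24% figures assume shifts of 0.1 / 0.2 / 0.3 SD, 36 per arm, a two-sided 5% test and no true effect. They show only that a modest shift would matter at this sample size. They also treat the whole shift as coming from the interview, whereas patients' own knowledge of their arm is a separate source that no change to the interviewer removes. Outcomes taken from the chart or data warehouse are not exposed to this route.

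This is a cheap improvement to a feasibility pilot, not a flaw that invalidates it.

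**What to change.** 1. State in the protocol that ARMS-D and/or ASK-12 are asked first in the post-visit call and saved in REDCap before any question on the assessment, portal, follow-up or acceptability.
2. Keep the arm hidden on the REDCap interview form until the scales are saved, then display it so that the intervention-only block can be given.
3. Where more than one existing coordinator is available, have the call made by one who did not randomise that patient. If only one is available, items 1 and 2 still apply.
4. Interpret the adherence result as unblinded self-report, since patients know whether they received the assessment.

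The cost is minor form work and, for item 3, some scheduling effort. No extra patients, visits, instruments or staff are needed, and the sample size stays at 80 accrued and at least 72 analysed. The change removes only the interviewer and question-order part of the bias.
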